One lab tech will be assigned to run the hematology analyzer using purple top vacutainer#1 and the leftover sample will be refrigerated in the same vacutainer and transported to PGIMER. (Figure 10)

[figure not shown]
Two lab techs will be assigned to make whole blood lysates (see SOP for making lysates) first and then centrifuge the leftover sample for plasma. Aliquots will be made as shown below. (Figure 11)

Purple Top #2 –Vacutainer – makelysates and centrifuge the rest for plasma. Aliquot into 4 cryovials

The fourth lab tech will centrifuge the yellow top vacutainer for serum and aliquot into 6 cryovials as shown below (Figure 12)

Yellow Top Vacutainer – centrifuge for serum and aliquot into 6 cryovials

After placing the samples in appropriate boxes, lab techs will place a check mark in appropriate places in the transmittal form. The boxes will have to be manually numbered and the box number has to be recorded in the transmittal form.

The leftover samples in one purple top vacutainer and the yellow top vacutainer should be kept refrigerated in a large Ziploc bag and transported to PGIMER.

13 Sorting Cryovials into Cryovial Boxes

[figure not shown]
Cryovials must be sorted properly into cryovial boxes according to specimen type. This is essential to ensure the correct specimens are shipped to the correct laboratory for processing. Laboratory Technicians are responsible for sorting the cryovials into the correct cryovial boxes according to specimen type during the processing of specimens. Once the Hematology is completed, the lab tech will place the purple vac #1 in the fridge and place a check mark in the transmittal form.

All cryovials need to be sorted in the following order. Also see Figure 8.

- Serum Folate and Vitamin B12 will be arranged in one box.
- Serum Ferritin and sTfR in one box
- Serum CRP and extra serum vials in one box. 0
- WBL Folate and WBL Extra in one box. 0
- Plasma Homocysteine and Extra plasma vial in one box.

A total of 5 cryovial boxes will be transported in the portable freezer, and 1 Vacutainer rack will be transported in the cold box to PGIMER every 2 days.

Figure 13: Sorting of cryovials in boxes.

Box samples by test, store boxes at -20°C till transporting to PGIMER lab (twice a week)

14 Transportation of Specimens from MPL to TFNC Lab

Every 2 days (cold chain logistics):

The supervisor, with the assistance of the Lab Technicians, is responsible for ensuring that all the specimens are consolidated and transferred to the laboratory for storage.

All processed specimens will be transported in the portable freezer except one purple top vacutainer rack which will be transported in the cold box. Sufficient gel packs need to be placed in the cold box to ensure the cold box is maintained at less than 8°C until it reaches TFNC laboratory. Transmittal forms from 2 days of blood collection will be placed in file folder and be transported along with the specimens.

- The team supervisor should ensure that the specimens reach TFNC laboratory and are stored appropriately.
- •____All of the gel packs used in the field should be frozen until they are hard every night.
- •____The freezer must be set to at least -20° C.
- It is critical the gel packs are completely frozen until hard before teams leave for the field each day.
- The leftover samples from one purple top and one yellow top vacutainer have to be transported to TFNC laboratory along in a cold box.

15 Lab Procedures for Specimen Storage

- All specimens except the vacutainer rack need to be stored properly in a -70°C freezer until they are analyzed.
- Cryovial boxes will be numbered numerically so that the specimen inside the box can be assigned to a specific cryovial box for the specimen inventory.
 - Box numbers will be assigned once specimens are processed at NPL.
- A specimen inventory should be created for all specimen boxes and divided according to specimen type.
- All cryovial boxes will be stored in a dedicated freezer and the vacutainer rack will be stored in the fridge.
- Once samples arrive in TFNC laboratory, a resident Lab tech will ensure that all samples stated in the transmittal form have arrived.

16 Annexure 1: Universal Precautions

- 1. Universal precautions are defined by CDC as a set of precautions designed to prevent transmission of human immunodeficiency virus (HIV), Hepatitis B virus (HBV), and other blood-borne pathogens.
- 2. Blood and other patients' body fluids are considered potentially infectious for HIV, HBV, and other blood-borne pathogens.
- 3. Therefore health-care workers who handle body fluids such as blood, mucus, sputum, urine, stool, etc. should observe the following precautions:
 - Prevent skin and mucous-membrane exposure when handling blood or other blood-borne pathogens.
 - Use personal protection barriers (e.g. gloves, lab coats and eye glasses).
 - Wash hands after removing the gloves.
 - Clean laboratory benches before and after procedures with an appropriate disinfectant.
 - Dispose needles in sharps containers to prevent injuries.
 - Dispose cuvettes and all other used materials in biohazard bags for incineration or appropriate disposal.
 - Immediately report all accidents or injuries to your supervisor and follow the below precautionary measures:
 - In case of injury, it is necessary to squeeze the blood out of the injury, thoroughly wash the injury with soap and running water, cleanse the skin with 70% alcohol.
 - In case of contamination of hands with the blood, immediately wash the hands with warm water and soap.
 - In case blood gets to face, it should be thoroughly washed with warm water and soap.
 - Test the specimen of the source individual for HIV and hepatitis as early as possible (within 24 hours of exposure).
 - Document the following data, related to the nature of exposed, status of source individual & status of exposed health worker

- Name and data of the source individual.
- Time & date of exposure.
- Nature of exposure.
- Body site exposed.
- Infective status of the source.
- Previous testing & Immune status of the exposed health worker.
- Seek medical assistance as soon as possible

	17 Annexure 2: Cold Chain Logistics
	Fresh frozen gel packs MUST be used at the beginning of each day. The
	Lab Technicians must store the gel packs at -20° C in the portable freezer
	when not in use. Whenever possible, gel packs that have thawed while in
	the field must be replaced with fresh frozen gel packs (i.e., when
Frozen Gel	temperature of the cold box reaches 5-6°C call the Supervisor to have a
Packs	Driver deliver new frozen gel packs). At the end of the day, gel packs used
1 deks	in the field should be placed in the portable freezers and kept at least at
	-20°C so that they will be frozen and ready for the next day. A Driver will
	deliver the portable freezer to the laboratory to be plugged into electricity
	overnight. The Driver will then transport the portable freezer with frozen
	gel packs back to the field at the beginning of the following day.
	After blood collection, the Lab Technicians should place the labelled
	vacutainers in the vacutainer rack and place in the cold box containing
	frozen gel packs. Bubble wrap should be placed between the vacutainers
Vacutainers	and the frozen gel packs so that they do not touch. There will be 2 purple
	top vacutainers and one yellow top vacutainer. All the specimens in the cold
	box and the portable freezer must be sent at the end of the day for
	processing and storage.
	The Lab Technicians should keep the cold box closed at all times. Avoid
	leaving the lid open and exposure to direct sun. A digital thermometer will
Cold Boxes	be included in each cold box. The temperature of the cold box should
	remain $<8^{\circ}$ C. When temperature of the cold box reaches $\sim6^{\circ}$ C call the
	Supervisor to have a Driver deliver new frozen gel packs.
	The purple top vacutainer #1 for measuring: 1) Hemoglobin/CBC using the
Purple Top	automated hematology analyzer at MPL 2) Reticulocyte count at MPL if
Vacutainer#1	necessary. 3) DNA extraction for MTHFR. Extracted DNA will be stored in
	labeled Eppendorf tubes after completing the extraction procedure.
Purple Top	The purple top vacutainer #2 will be used to make 1) WBL for the Folate
Vacutainer#2	microbiological assay 2) Backup of WBL. Then the vacutainer will be spun

17 Annexure 2: Cold Chain Logistics

	down in the centrifuge for 3) Plasma HCY 4) Back up vial for Plasma.
Yellow Top Vacutainer	The yellow top vacutainer needs to be spun down for serum using the centrifuge and then aliquoted into 4 cryovials and 1 PCR vial for 1) Serum Folate, 2) Serum B12, 3) Serum Retinol, 4) Back-up vial for serum, 5) PCR vial for Ferritin, sTfR, CRP, AGP, RBP

19 Four teams will collect 21 samples from each village, $n = 21$						
	21 households per village (plus extra supplies)					
Supply Item	Quantity Required					
Backpack	4					
Yellow Top Vacutainers	25 per team= 50 per day					
Purple Top Vacutainers	50 per team= 100 per day					
Tourniquet	2 per team= 4 (can be reused)					
21G Needles	25 per team= 50 per day					
Vacutainer Barrels	4 per team (can be reused)					
Sharps container	1 Box each= 2					
Alcohol pads	30 per team= 60 per day					
Gauze pads	30 per team= 60 per day					
Absorbent pads	2 (can be reused if clean)					
Biohazard bags	2					
Ziploc bags	15 small per team= 30 per day					
Labels	3 sets pre-printed per subject= 25 sets					
Cold box	1 per team= 2					
Frozen Gel Packs	4-5 for each cold box= 10					
Bubble Wrap	2Large Piece (to protect specimens from frozen gel packs inside each cold box)					
	1 each for cold box $=2$					
Digital Thermometer						
Vacutainer Rack for						
Cold Box	1 each per box					
Kim wipes	1 Box each = 2 boxes					
Band-Aids	30					
Gloves S, M, L	1 Box each per team of correct size (with a minimum of 30 pairs)					
Pens	2					
Log note books	4 (1 each)					

Annexure 3: List of Supplies Needed Daily for Specimen Collection 9 Four teams will collect 21 samples from each village, n = 21

21 Annexure 4: Freezer Temperature Monitoring Form(-20^oC)

District/Region:

Survey Laboratory Coordinator:

Field Laboratory Technician:

Freezer Information (i.e., type)

- 1.) To be used to monitor freezers located in the field laboratory at Morogoro.
- 2.) Please monitor the temperature of the freezer daily and record the date, time, temperature, initials, and any observed issues with the operation of the freezer.
- 3.) Report any issues to the Survey Laboratory Coordinator.
- 4.) Freezers will only be used to store specimens: a) until they are transferred to TFNC, Dar-Es-Salaam.
- 5.) Do not store processed specimens in refrigerators!

Date	Time	Temp., °C	Initials	Observations

22

23

24 Annexure 5: Refrigerator Temperature Monitoring Form (1°- 6°C)

District/Region:
Survey Laboratory Coordinator:
Field Laboratory Technician:
Refrigerator Information (i.e., type)

1.) To be used to monitor refrigerators located in Field laboratory at Morogoro.

- 2.) Please monitor the temperature of the refrigerator daily and record the date, time, temperature, initials, and any observed issues with the operation of the refrigerator.
- 3.) Report any issues to the Survey Laboratory Coordinator.

4.) Refrigerators will only be used to keeping samples, reagents and quality control material.

Date	Time	Temp., °C	Initials	Observations
			1	

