4.1 Data Collection

Morogoro Region Micronutrient Household and Biomarker Survey

The survey will be conducted on a sample of households selected from all seven districts in the Morogoro region. Data will be collected on electronic tablets.

Criteria for inclusion/exclusion of subjects include:

- *i.* Inclusion criteria for study participants
 - a. Household residents who are present in their households at the time of the interview (or during 2 additional visits the same day)
 - b. Household has resided in current dwelling for at least 3 months
 - c. Individuals who consent to participate in the survey and prepare or purchase food for the household
 - d. At least one non-pregnant WRA (15-49 years) residing in the household
- *ii.* Exclusion criteria for study participants
 - a. Any household that does not meet inclusion criteria will be excluded.

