4.4 Sampling Procedure and Sample Allocation

This is a cross-sectional household-based survey with a sample size of 1170 non-pregnant women of reproductive age. The Morogoro region encompasses seven districts, and 45 clusters will be selected from all districts (20 from urban strata and 25 from rural strata).

Data from the 2012 Tanzania Population and Housing Census for the Morogoro region (Table 2) will provide the sampling frame for this survey. Because regional differences in the distribution of rural compared with urban populations in the region, a stratified, multistage probability sample will be used for urban and rural areas. This survey will allow for independent estimates for WRA (Henderson & Sundaresan, 1982). The first stage of the sample design will be the selection of enumeration areas (EA) with probability proportional to size (PPS) design (20 urban and 25 rural areas) (Lemeshow & Robinson, 1985). The Probability Proportional to Size (PPS) design will ensure proper representation by district and population distribution. In the second stage, 26 households will be selected from each EA (totaling 1170 women). To select the households, household listing and maps of their location will be conducted in all the selected EAs prior to the initiation of survey data collection. A household listing form will be used to identify and select eligible households. A two-member team, comprising one mapper and one lister, will visit each EA to locate and mark its physical boundaries. The mapping team will do a census of all households and prepare a list of households with the name of the head and address or location of each household. During household listing, a list of household members, including the individual who prepares and/or purchases food for the household and WRA between 15 - 49years of age. In order to ensure that the household listing is current and to minimize nonresponse, the time period between household listing and the start of data collection will not exceed one month. Only one WRA participant per household will be selected.

The survey findings will be generalizable to the Morogoro region.

Table 2: Distribution of Morogoro región households, number of EAs by district and by type of residence (Census 2012).

District	Number	of Househo	olds	Number	of EAs	
	Rural	Urban	Total	Rural	Urban	Total
Kilosa	71836	30079	101915	762	358	1120
Morogoro	2328	73019	75345	24	688	712
Municipal						
Morogoro Rural	70369	3021	73390	756	30	786

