8.3 Field and laboratory protocol

Protocol for Specimen Collection, Processing, Storage, Shipment and laboratory analysis

Morogoro Regional Micronutrient Household and Biomarker Survey, Tanzania

2019

Acronyms

TFNC	Tanzania Food and Nutrition Centre
AHL	Average House Listing
ANM	Auxiliary Nurse Midwife
APL	Above Poverty Line
ASHAs	Accredited Social Health Activists
BPL	Below Poverty Line
CDC	Centers for Disease Control and Prevention
CHC	Community Health Centre
DBC	Designing for Behaviour Change
DNA	Deoxyribonucleic Acid
EB	Enumeration Block
FFI	Food Fortification Initiative
FGD	Focus Group Discussion
GAIN	Global Alliance for Improved Nutrition
ICDS	Integrated Child Development Services
IDD	Iodine Deficiency Disorders
IRB	Institutional Review Board
IT	Information Technology
MDD	Micronutrient Deficiency Disorders
MI	Micronutrient Initiative
MTHFR	Methylene tetrahydrofolate reductase
NFHS	National Family Health Survey
NGO	Non-Government Organization
NHM	National Health Mission
MPL	Morogoro Processing Lab
NPWRA	Non-Pregnant Woman of Reproductive Ag (18-49 years)
NTDs	Neural Tube Defects
OBC	Other Backward Classes
OPH	Other Priority Households
PDS	Public Distribution System
PGIMER	Post Graduate Institute of Medical Education and Research
PHC	Primary Health Centre
PPS	Probability proportional to Size sampling
PSU	Primary Sampling Unit
RBC	Red Blood Cell
SC	Scheduled Class
WCD	Women and Child Development
WHO	World Health Organization
WFP	World Food Program

Lab Specific Acronyms:

AA	Ascorbic acid
CRP	C - reactive protein
HCY	Homocysteine
HPLC	High performance Liquid Chromatography
sTfR	Serum Transferrin Receptor
MPL	Morogoro Processing Lab
S. B12	Serum B 12
S.Folate	Serum Folate
SOP	Standard Operating Procedures
WBL	Whole Blood Lysate

PART I – Specimen collection and Processing

INTRODUCTION

This manual covers the field and laboratory components of the Tanzania Food and Nutrition Survey. It describes field procedures such as specimen collection and processing and sample storage by aliquot as per test requirement at Morogoro lab, as well as laboratory analysis by the Tanzania Food and Nutrition Centre, Dar-Es-Salaam, Tanzania.

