This training manual is to serve as a detailed guide for the survey laboratory personnel who will be recruited for sample collection, processing and laboratory analysis. The manual provides detailed methodology for field procedures, including universal precautions, labeling, specimen collection and processing, sample storage and transportation, and management of the cold chain. This guide should be read carefully prior to the field work, and any questions should be discussed with the survey coordinator, principal investigators, laboratory coordinator and CDC technical support team.

There will be one survey team, consisting of one supervisor, four interviewers, and four lab technicians. The study will consist of 55 villages (clusters) and 21 households will be visited per village to recruit one non-pregnant woman aged 18-49 years per household for a total of 790 participants. Each survey team will visit one village per day to interview 21 women each. After

interviewers complete the questionnaire, a lab technician will collect blood after informed consent. Two lab technicians will carry out blood collection into pre - labelled vacutainers (two purple-top and one yellow-top) after verification of the participant. After completion of blood collection from about 12 participants (approximately 3-4 hours), blood specimens will be transported to Morogoro processing laboratory. There, specimens will be processed, aliquoted and stored according to the details given below on the same afternoon. Twice a week the specimens both refrigerated and frozen, will be transported maintaining the appropriate cold chain requirement to the TFNC in Dar-Es-Salaam for laboratory analysis by various biochemical tests. Arrangements for sample collection for the next day should be completed the previous afternoon by the laboratory personnel.

Biomarker	Condition or nutrient
Hemoglobin	Anemia
Erythrocyte folate	Folate
Serum folate	Folate
Serum vitamin B12	Vitamin B12
Serum ferritin	Iron
Soluble transferrin receptor	Iron
Alpha 1 acid Glycoprotein	Inflammation
C-reactive protein	Inflammation
Retinol Binding Protein	Vitamin A
Retifior Diffaing Frotein	
MTHFR	Folate/one-carbon metabolism
Homocysteine	Vitamin B12 and folate

Table 1: Baseline Biomarker Assessment: Laboratory Analyses and Indicators

Overall Universal Precautions and Considerations

- Collection, testing, and processing of biological specimens are critical parts of the Micronutrient Survey.

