- The interviewer is responsible for:
 - Conducting the HH interview.
 - Assigning a lab ID and label the questionnaire columns for those eligible in the HH.
 - Requesting informed consent to participate in blood collection.
- The laboratory personnel are responsible for:
 - Organization of supplies needed for specimen collection in the field every day (Annex 3).
 - Each day enough supplies need to be available for a total of 21 blood draws per day (plus 10% extra supplies).
 - Cleaning working area prior to specimen collection.
 - Performing venipuncture on selected participants.
 - Maintenance of cold chain in the field (Annex 2)
 - Specimen collection at the houshold and transporting samples to Morogoro Processing lab. (Annex 8: Flow Chart for Specimen collection and processing at Morogoro Processing Lab)
 - Conducting complete blood count testing using the automated hematology analyzer at Morogoro Processing Lab.
 - Alerting participants with Hemoglobin less than < 8 gms/dl to go to the nearest PHC for evaluation and treatment by a clinician.
 - Making whole blood lysates and aliquoting them into 2 cryovials.
 - Centrifuge yellow top serum separator and aliquot them into 6 cryovials.
 - Maintenance of cold chain in the field and at Morogoro.
 - Recording participant label and specimen information on transmittal sheet. (Annex 3a)
 - Ensure labels are appropriately used and forms completed correctly
 - Understand all aspects of data collection and conduct field testing.
 - Ensure the Hematology analyzer, centrifuge and other equipment are calibrated and functioning properly.
 - Keep in daily contact with the regional coordinator and team supervisor during field work.
 - Make sure the necessary supplies and equipment are ready the night before each day of field work.
 - Manage the work flow in the processing lab and maintain all documentation regarding the completion of the cluster.
 - Ensure labels are appropriately used and forms completed correctly.

- o Review all data collection forms for consistency and completeness,
- Serve as back-up and assist team members if they need help.
- Ensure any difficulties with equipment/supplies are communicated to the team supervisor /coordinator as soon as possible.
- Troubleshoot any problems with fieldwork, request support if needed.
- Remaining flexible for accepting any reasonable tasks assigned that are not listed above
- A flowchart of responsibilities for the Lab technicians is located in Annex 15.

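### Section 4.4 and the field manual in Appendix 8.3 give two unreconciled designs (45 EAs x 26 households, ages 15-49; 55 clusters x 21 households, ages 18-49); the lower age limit is the main risk

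*Protocol*

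**What the plan says.** **Main text.** Protocol section 4.4 states that "45 clusters will be selected from all districts (20 from urban strata and 25 from rural strata" and continues: "In the second stage, 26 households will be selected from each EA (totaling 1170 women". Appendix B repeats 45 areas, 26 households and 1170 women. On age, the inclusion criterion in section 4.1 reads "At least one non-pregnant WRA (15-49 years) residing in the household"; the primary objective in section 3, the household listing in section 4.4 and the criteria in Appendix B use the same range.

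**Field and laboratory manual (Appendix 8.3).** The Part I introduction reads "The study will consist of 55 villages (clusters) and 21 households will be visited per village to recruit one non-pregnant woman aged 18-49 years" and gives the sum as "for a total of 790 participants". This is more than one slip:

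- The acronym list defines the target woman as "Non-Pregnant Woman of Reproductive Ag (18-49 years".
- The cold-chain overview (manual section 10) again says 55 villages.
- Manual section 11 says "Each day enough supplies need to be available for a total of 21 blood draws per day (plus 10% extra supplies".
- The field rack layout ends at donor 21, and Annexure 3 is headed for 21 samples per village.
- The example labels in manual section 12 carry the age range 15-49, so the manual also disagrees with itself.

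The manual is titled for the 2019 Morogoro survey, and sections 4.5 and 4.6 refer to it for specimen procedures. It is current text, not a record of superseded wording.

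**The concern.** The number of clusters, the take per cluster and the age range together define the sample and the population it represents. Here one protocol gives two values for each, with no statement of which prevails.

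Two things are at stake. The first is coverage. The primary objective concerns non-pregnant women aged 15-49. A team that screens at 18 leaves out a defined part of that population, and no weight can be attached to women who could never be selected.

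The second is the selection probability. Sections 4.4 and 8.2 set the sampling interval as the number of houses in the EA divided by the number to be interviewed, which is 26. A team that works down that list and stops at 21 leaves the last selections in list order unvisited.

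**Working it through.** **1. The plan's own totals.**
- Section 4.4: 45 x 26 = 1170, as stated.
- Precision formula with the section 4.2 inputs (prevalence 50%, margin 5%, 95% confidence, design effect 2, response 68%): 1.96² x 0.25 / 0.05² = 384.1; x 2 = 768.3; / 0.68 = 1130. The 1170 is 40 above this, so the formula gives 3.4% less than the plan's figure.
- Manual: 55 x 21 = 1155, not 790.

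**2. What 790 may be.** 790 / 1155 = 68.4%, and 1155 x 0.68 = 785. The figure fits expected respondents at the section 4.2 response rate. The manual does not say so.

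**3. Like-for-like comparison.** Respondents = selected x 0.68. Half-width = 1.96 x √(0.25 x 2 / respondents).

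| Design | Selected | Expected respondents | Half-width, design effect 2 |
|---|---|---|---|
| 45 x 26 (section 4.4) | 1170 | 796 | 4.91% |
| 55 x 21 (manual) | 1155 | 785 | 4.95% |
| 45 x 21 (mixture, in neither text) | 945 | 643 | 5.47% |

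The two written designs differ by 15 households (1.3%), and both meet the 5% margin.

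**4. Allowing for the smaller take.** A design effect of 2 at 26 x 0.68 = 17.7 respondents per EA implies an intra-EA correlation of (2 - 1) / (17.7 - 1) = 0.060. At 21 x 0.68 = 14.3 per cluster, the design effect becomes 1 + 13.3 x 0.060 = 1.80. The half-width is then 4.69% for 55 x 21 and 5.18% for the 45 x 21 mixture. The ordering is unchanged: only the mixture misses 5%.

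**5. Age.** Ages 15-49 span 35 single years, of which 15-17 are three: 3 / 35 = 8.6%. This assumes equal numbers at each age; the documents give no age distribution. Excluding a share of 0.086 moves the prevalence by 0.086 x (prevalence at 18-49 minus prevalence at 15-17), or about 0.09 points for each point of difference. The documents give no prevalence by age, so the size of the shift cannot be fixed.

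**6. Stopping early.** (26 - 21) / 26 = 19% of the selected households in an EA would go unvisited.

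**7. Supplies.** Manual section 11 implies 21 x 1.1 = 23 draws a day. Annexure 3 lists more: 25 yellow tubes per team and 50 per day, with purple tubes and needles to match. At 68% response, 26 households yield about 18 draws. Only the 25 label sets and the 21-donor rack layout fall below 26.

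**The case against.** The strongest reply is that the manual does not govern selection. It addresses laboratory personnel. Households are chosen under section 4.4 and Appendix B, both of which say 26, from a listing of women aged 15-49, and the manual's own labels carry that range. Section 4.4 also plans a spreadsheet of sampling parameters and selection probabilities, so a different take that was planned and recorded would not by itself make the weights wrong. The manual's acronym list contains terms from another setting, which suggests carried-over text rather than a rival design.

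Most of this stands, and it makes the harm conditional. It does not remove the contradiction. The manual also directs interviewers: it sets 21 women per village-day and has them label questionnaires for eligible household members and request consent to blood collection. Staff are told to read it carefully before fieldwork.

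Several stronger readings are tempting but unsupported:

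- **790 against 1170 as a loss of one third.** The first is plausibly a count of respondents and the second a count of selected women. The fault is an unlabelled total.
- **The manual's design misses the 5% margin.** It does not; only the 45 x 21 mixture does, and neither text specifies that.
- **Kits would run short.** Annexure 3 lists enough tubes and needles for 26 draws.
- **Urban areas are left out because the manual says villages.** The manual glosses the word as clusters.

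**Conclusion.** The contradiction is real in three elements: cluster number, households per cluster and lower age limit. It should be settled before training.

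It is not a precision problem. The two designs give 4.91% and 4.95% under the protocol's own assumptions of 50% prevalence, design effect 2 and 68% response. A margin of about 5.5% arises only if the 45 EAs of one text are combined with the 21 households of the other.

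The age limit matters most. If 18-49 were applied, women aged 15-17 (about 8.6% of the target population under uniform ages) would have zero selection probability, and the estimates would describe a narrower population than the primary objective names. The documents do not show that this will happen; they show that staff hold conflicting instructions. Stopping at 21 of 26 selected households comes second, and is harmful mainly where the interval was set for 26 or practice differs between EAs.

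**What to change.** Before training, bring the manual into line with section 4.4 and Appendix B: 45 EAs (20 urban, 25 rural), 26 households per EA and women aged 15-49. The places to change in Appendix 8.3 are the acronym list, the Part I introduction, manual sections 10 and 11, the supplies line for 21 women, the rack layout and Annexure 3.

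Label each total as selected (1170) or expected to respond (about 796). Match the label sets and rack layout to the chosen take.

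If 55 x 21 is what the sponsor intends, change section 4.2, section 4.4, Appendix B and the weights instead, and keep ages 15-49. Only one design should remain.

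A separate editorial point, with no bearing on the sample: manual section 13 says "1 Vacutainer rack will be transported in the cold box to PGIMER every 2 days", while the Part I introduction and manual section 14 send specimens to TFNC. These destinations need reconciling.

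The cost is text editing and a few more label sets per cluster. After fieldwork, an excluded age group could not be recovered.
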